10. SAFETY

10.1 Medical Device Category C studies

All adverse events (AE) including all serious adverse events (SAE) are collected, fully investigated and documented in the source document and appropriate case report form (CRF) during the entire study period, i.e. from patient's informed consent until the last protocol-specific procedure, including a safety follow-up period. Documentation includes dates of event, treatment, resolution, assessment of seriousness and causal relationship to device and/or study procedure.

The information on AEs is systematically collected by the clinician at each study visit. They will follow the procedures outlined in SOP-Medical Device Incident Reporting. The subjects are asked to keep a diary and write down any unexpected events. During the regular clinic visits the subjects are then asked questions about the event to gather details and to determine the severity of the event. If a subject reports pain that results in the inability to use the device he will be withdrawn from the study in order to avoid any pain from using the device and to remove partial data from the study. For reports of pain caused by insertion or the dome itself, the problem can be addressed in the clinic. For example, a different style or size of dome can be placed on the hearing aid, and re-training of insertion can be performed with the subject to avoid wrong or forceful insertion of the device. For reported pain they will be advised to not wear the device for 24 hours before resuming use.

Foreseeable adverse events outlined in the risk management file include discomfort caused by the domes, domes or filters falling off in the ear, no amplification coming from the device causing alarms or traffic to not be heard by the subject, skin reaction if chemical profile of device is changed, maximum output of the device exceeding 132 dB SPL, battery exploding or catching fire, and the device affecting other medical devices worn by the subject. The incidence of all of these risks or adverse events is improbable. To mitigate the risk, the IFU describes how to insert the device, how to change the domes, and how to change a battery in case of no amplification. The IFU describes how to clean the device, domes, and filters in order to not introduce cleaning agents that might change the chemical profile of the hardware of the device. The labelling warns of the potential maximum output of the device. The IFU instructs the user to keep the device away from explosive environments, The IFU warns of interference with implantable devices.

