7.4 Criteria for withdrawal / discontinuation of participants

Participants are allowed to withdraw from the study at any time and for any reason. They do not have to share the reasons with the investigator. They will be asked to return the IMD. If the decision to withdraw is made by the investigator, the PI will inform the subject in person that they are no longer needed for the study. Reasons for withdrawing a participant from the study could be for non-compliance during testing, unreliable responses, medical reasons such as an ear infection, or the study may need to be stopped or postponed. Any data gathered from these subjects will be used for the current study. All data will remain encoded because results are only recorded using the identification code of the subject. There are normally at least five “back-up” test participants on the list to replace those that withdraw or are withdrawn. The “back-up” participants have already been screened and deemed to be appropriate for the study.

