8.3 Device modifications

The IMD will provide the similar amplification as the RMD; therefore, the subject should not experience any significant negative differences that would make the subjects want to discontinue use of the device. However, if a subject does report such differences, that can be improved with fine tuning, fine tuning can be made to improve the situation enough for the subject to continue with the study. If the subject requests to discontinue they can immediately remove the IMD from their ear and return to using their own BTEs. They will be asked to return the IMD to Bernafon AG, but their data will still be included in the results for the current study. All data will remain encoded because the results are only recorded using the identification code of the subject.

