8.5 Data Collection and Follow-up for withdrawn participants

Any data that is collected will be kept in the data management database. The data will remain encoded because results are only recorded using the identification code of the subject. The analysis and report will include a section based on the data available from all recruited subjects (as the intention to treat ITT) and another section based on the data from the subjects that complete the entire protocol (per protocol PP). Withdrawn subjects will have the same follow-up as those subjects that complete the trial. As all subjects are taken from the Bernafon database, all participants, including those that withdraw, are welcome to return to the clinic for fine-tuning and maintenance as needed.

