11.5 Handling of missing data and drop-outs

For missing data, the PI will contact the involved subject to evaluate the possibility of getting missing data from a questionnaire by post. If a test subject cannot come to the evaluation visit, after exhausting all the possibilities to reschedule a new one, the devices will be sent back per post. If a subject does not want to adhere to the protocol, he can easily switch back to his own devices and return the IMD.

Dropouts will not be replaced; therefore, extra subjects over the calculated sample amount will be included from the beginning to ensure enough completed cases with all data.

The analysis and report will include two separate sections. The first section is based on data from all recruited subjects (as the intention to treat ITT part) and the second section is based on the data from subjects that complete the entire protocol (per protocol PP). Demographical and audiological data (e.g. hearing loss thresholds, degree, and classification) will be available from all recruited subjects including the withdrawn subjects and will be analysed in the report.

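### Section 10.1 makes removal of partial data a purpose of withdrawing subjects for pain, against the retention rules in 7.4, 8.3, 8.5 and 11.5; 7.4 and 11.5 also disagree on replacement

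*Protocol*

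**What the plan says.** Section 10.1 covers a subject whose pain makes the device unusable. That subject is to be "withdrawn from the study in order to avoid any pain from using the device and to remove partial data from the study". Two purposes are given: sparing the subject pain, and taking incomplete data out of the study.

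Other sections set a different rule for the data:

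- Section 7.4 covers participants who leave by choice and those withdrawn by the investigator, with medical reasons among its examples: "Any data gathered from these subjects will be used for the current study".
- Section 8.3 covers a subject who asks to stop using the IMD and returns it: "their data will still be included in the results for the current study".
- Section 8.5 covers withdrawn participants in general: "Any data that is collected will be kept in the data management database".
- Section 11.5 divides the report in two: "The first section is based on data from all recruited subjects (as the intention to treat ITT part"; the second section covers subjects who complete the whole protocol. Section 8.5 describes the same split.

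On filling vacated places, section 7.4 describes back-up "test participants on the list to replace those that withdraw or are withdrawn", whereas section 11.5 states: "Dropouts will not be replaced". It relies instead on recruiting extra subjects from the start.

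**The concern.** The removal in 10.1 depends on an outcome. It applies only to subjects who cannot use a device because it hurts. Comfort is among the secondary outcomes (5.2) and discomfort among the safety outcomes (5.3), so the data to be removed come from subjects with a poor result on something the study measures.

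These subjects are already outside the per-protocol set, which 11.4.1 names as the analysis population, because they do not complete the protocol. The all-recruited section is the one place where their results can be seen. If 10.1 takes them out of that section too, their speech and questionnaire results appear nowhere in the report. Section 11.4.5 rests the safety analysis on a participant questionnaire together with the investigator's clinical judgement, so losing completed questionnaires affects a named source of that analysis.

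The conflict over replacement adds a second uncertainty: whether the place of a withdrawn subject is left empty or filled.

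**Working it through.** This is mainly a comparison of texts.

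**1. Can the rules be followed together?** Section 7.4 includes withdrawal by the investigator for medical reasons, which is the situation in 10.1. For that subject 7.4 says the data are used, and 10.1 gives removing them as a purpose. No carve-out for pain appears in 7.4, 8.3, 8.5 or 11.5. The conflict also produces an arbitrary result: a subject in pain who asks to stop the IMD falls under 8.3 and the data stay, while a subject with the same pain who is withdrawn under 10.1 loses the partial data.

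**2. Which data exist at the time of withdrawal?** From the visit procedures in 9.3.1 to 9.3.3:

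| Pain stops device use | Outcome data that may already exist | Not yet collected |
|---|---|---|
| During RMD wear, before visit 2 | RMD APHAB and product questionnaires, if completed | All speech tests, all IMD questionnaires, preference |
| During IMD wear, between visits 2 and 3 | OLSA in all three conditions; RMD APHAB and product questionnaires; IMD questionnaires only if already completed at home | GÖSA, preference |

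A subject who stops in the second period would normally have a complete OLSA set, which is the primary measurement. Data in the last column would be missing under any rule.

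**3. What happens to the all-recruited section?** It adds information to the completers' section only through non-completers' data. For OLSA, those are subjects tested at visit 2 who do not finish. If every such subject left because of pain and 10.1 were applied, the OLSA results in the two sections would be identical.

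**4. Size.** The synopsis plans about 15 to 20 participants. One subject is 1/20 = 5.0% to 1/15 = 6.7% of the sample. The protocol gives no expected rate of withdrawal for pain, so no total can be computed.

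**5. Power.** Section 11.2 uses n = (σ(z₁₋α + z₁₋β)/δ)² with σ = 1.6 dB, δ = 1 dB, α = 0.05 and power 0.80: (1.6 × (1.645 + 0.842)/1)² = 15.83, rounded up to 16. The stated figure reproduces. By the same normal approximation, power is 87.5% at n = 20, 80.4% at 16 and 78.1% at 15, so four losses from 20 still leave 16. In any case the per-protocol set loses non-completers by its own definition, whatever 10.1 says. Power is not the issue; selective loss from the all-recruited section is.

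**6. Direction.** Section 10.1 speaks of the device without saying which, and its text on pain refers to domes, which 8.1.1 and 8.2.2 assign to the BTE reference device. Removing a completed IMD questionnaire that reports pain would favour the IMD. Removing a completed RMD questionnaire that reports pain would favour the RMD. For the OLSA set, nothing in the protocol links later wearing pain to the SRT difference measured at fitting.

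**The case against.** The strongest reply is that 10.1 sits in the safety chapter and states a purpose of withdrawal, not a deletion procedure. The data rules are in 7.4, 8.3, 8.5 and 11.5, they agree with one another, and 10.1 could mean only that the subject leaves the per-protocol set. That reading is possible, but 10.1 speaks of removing data from the study, not from one analysis set. The ambiguity is itself the defect.

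Three stronger readings are tempting and are not supported:

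- *The pain events disappear from the safety record.* Section 10.1 itself requires every adverse event to be recorded in the source document and CRF, 9.2.3.1 has subjects asked whether the event was painful or uncomfortable, and 12.1.2 requires a CRF for subjects who do not finish, with the reason for withdrawal. Pain withdrawals should remain countable.
- *The results are biased in favour of the IMD.* The clause can apply to either device. Participants have worn BTE aids for at least 6 months, which makes new pain with the ITE more plausible, but that is inference. Preference and many IMD questionnaires would not yet exist, so their absence would not come from 10.1.
- *Pain cases are removed and replaced, leaving an apparently clean sample.* This needs the harsh reading of 10.1 and also needs 7.4 to override 11.5, which is explicit. The protocol gives no counts from which to size such an effect.

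**Conclusion.** The contradiction stands. Section 10.1 gives as a purpose the removal of data that 7.4, 8.3 and 8.5 say are used, included and kept, and that the all-recruited section in 8.5 and 11.5 needs. If 10.1 is followed, exclusion depends on an outcome. It affects speech data, up to a complete OLSA set, and any completed APHAB or product questionnaires, at 5.0% to 6.7% of the planned sample per subject. The total depends on how many subjects stop because of pain, which the protocol does not estimate, and the direction depends on which device caused it. The per-protocol analysis and its power do not change through 10.1, given that per protocol means completing the whole protocol. The disagreement between 7.4 and 11.5 on replacement is a separate inconsistency that also needs resolving.

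**What to change.** - In 10.1, delete the second stated purpose of withdrawal, the removal of partial data. Leave the clinical rule on when a subject is withdrawn as it is.
- State in 10.1, or by reference to 8.5, that all speech, questionnaire and adverse event data collected up to withdrawal stay in the all-recruited section, and that withdrawals for pain are reported by device (RMD or IMD).
- Reconcile 7.4 with 11.5 so that the protocol gives one answer on whether withdrawn subjects are replaced. Under either answer, the withdrawn subject's data stay in the all-recruited section.

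The cost is a few wording edits, handled under the amendment procedure in 2.10. No extra visits, measurements or subjects are needed. The new wording does not recover assessments that a subject never reached; those remain missing data.

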10.1.1 Definition and Assessment of (Serious) Adverse Events and other safety related events

Adverse Event (AE)

Any untoward medical occurrence, unintended disease or injury or any untoward clinical signs (including an abnormal laboratory finding) in participants, users or other persons whether or not related to the investigational medical device [ISO 14155: 3.2].

This includes events related to the IMD or the RMD and to the procedures involved. For users or other persons this is restricted to events related to the IMD.

Adverse Device Effect (ADE)

Adverse event related to the use of an investigational medical device [ISO 14155: 3.1].

This includes any adverse event resulting from insufficient or inadequate instructions for use, deployment, implantation, installation, operation, or any malfunction of the investigational medical device. This includes any event that is a result of a use error or intentional misuse.

AEs/ADEs include:

- Exacerbation of a pre-existing disease or condition.
- Increase in the frequency or intensity of a pre-existing episodic disease or medical condition.
- Any disease or medical condition detected or diagnosed after treatment with the study intervention device even though it may have been present yet undetected prior to the start of the clinical investigation.
- Any continuous persistent disease or symptoms present at baseline that worsen following the start of the clinical investigation.
- Events considered by the investigator to be related to any of the clinical investigation-mandated procedures.

- Abnormal assessments, e.g. physical examination findings, will be reported as AEs/ADEs if they represent a clinically significant finding that was not present at baseline or that has significantly worsened during the course of the clinical investigation.
- Test abnormalities will be reported as AEs/ADEs if they represent a clinically significant finding, symptomatic or not, which was not present at baseline or has significantly worsened during the course of the clinical investigation.

AEs/ADEs do not include:

- Pre-planned interventions or occurrences of endpoints specified in the CIP are not considered AEs/ADEs, if not defined otherwise.
- Unrelated medical or surgical procedures, e.g. surgery, endoscopy, tooth extraction, transfusion. However, the event leading to the procedure may be considered an AE. If this event is serious, the procedure will be described in the SAE/SADE narrative.
- Any pre-existing disease or medical condition that remains stable and does not worsen during the course of study participation.
- Situations in which an adverse change did not occur, e.g., hospitalizations for unrelated cosmetic elective surgery or for social and/or convenience reasons.

Serious Adverse Event (SAE)

Adverse event that:

- results in death, or
- led to a serious deterioration in health that either:
 - results in a life-threatening illness or injury, or
 - results in a permanent impairment of a body structure or a body function, or
 - required in-patient or prolonged hospitalisation, or
 - results in medical or surgical intervention to prevent life threatening illness, or
- led to fetal distress, death or a congenital abnormality or birth defect. [ISO 14155: 3.37].

This includes device deficiencies that might have led to a serious adverse event if a) suitable action had not been taken or b) intervention had not been made or c) if circumstances had been less fortunate. These are handled under the SAE reporting system. A planned hospitalization for pre-existing condition, or a procedure required by the protocol, without a serious deterioration in health, is not considered to be a serious adverse event.

Device deficiency

Inadequacy of a medical device related to its identity, quality, durability, reliability, safety or performance, such as malfunction, misuse or use error and inadequate labelling [ISO 14155: 3.15].

Health hazards that require measures

Findings in the trial that may affect the safety of study participants and, which require preventive or corrective measures intended to protect the health and safety of study participants [ClinO Art. 37].

Severity of adverse events/adverse device effects

The severity of clinical AEs is graded on a three-point scale: mild, moderate and severe, and reported in the CRF. If the severity of an AE worsens during medical device administration, only the worst intensity should be reported on the CRF. If the AE lessens in intensity, no change in the severity is required.

Mild: Event may be noticeable to subject; does not influence daily activities; the AE resolves spontaneously or may require minimal therapeutic intervention;

Moderate: Event may make subject uncomfortable; performance of daily activities may be influenced; intervention may be needed; the AE produces no sequelae.

Severe: Event may cause noticeable discomfort; usually interferes with daily activities; subject may not be able to continue in the study; the AE produces sequelae, which require prolonged therapeutic intervention.

Causal Relationship of SAE [MEDDEV 2.7/3 revision 3, May 2015].

A causal relationship towards the medical device or study procedure should be rated as follows:

- **Not related:** The relationship to the device or procedures can be excluded.
- **Unlikely:** The relationship with the use of the device seems not relevant and/or the event can be reasonably explained by another cause, but additional information may be obtained.
- **Possible:** The relationship with the use of the investigational device is weak but cannot be ruled out completely. Alternative causes are also possible.
- **Probable:** The relationship with the use of the investigational device seems relevant and/or the event cannot reasonably be explained by another cause.
- **Causal relationship:** The serious event is associated with the investigational device or with procedures beyond reasonable doubt.

Device deficiencies that might have led to an SAE are always related to the medical device.

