3.4 Clinical Evidence to Date

A clinical literature evaluation is maintained and has been updated in 2017. The basic benefit of hearing aids does not change with newly released devices. They are designed to amplify sound. The benefit of hearing aids has been shown in various studies (Kochkin, 2011). The evaluation includes an analysis of adverse events for Bernafon products as well as competitor devices that is used as post market analysis of the devices. The same Mermaid 9 device in a different hardware style was released to the market in early 2017. To date, there have been no adverse events reported on the U.S Food and Drug (FDA) Manufacturer and User Facility Device Experience (MAUDE) website.

Studies have concluded that different hearing aid styles can have an influence on comfort, occlusion, and feature functionality (Winkler et al., 2016). However, they all still provide the benefit of amplification.

A risk assessment is performed for all new devices. The primary risk identified is the possibility of over amplification from excessive sound pressure levels (further described in sec. 3.7). This risk is mediated by printing a warning in the Instructions for Use for hearing aids with high sound pressure level output capability. Additionally, when this type of instrument is selected in the software, there is a message warning the HCP of the sound pressure capability. Overall, Bernafon AG has had no adverse event reported in the last 16 years including no required modifications or recalls of products.

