3.7 Risks / Benefits

The audiological and psychoacoustic investigations are conducted using volunteer test participants with sound pressure levels that will not endanger their residual hearing. The test participants will be advised of the type, content, extent, and possible risks of the test beforehand. As psychometric methods are involved in the data collection, the risk for the test participants is judged to be extremely minor. However, the following risks shall be addressed:

Risk of hearing loss to residual hearing at too high a level in audiological and psychoacoustic experiments: Due to the test design (use of noise level up to a maximum of 100 dB SPL) and the hardware limitations of the measuring equipment (maximum output of loud speaker) the maximum provided sound level is restricted. During audiometry (test of hearing loss with audiometer) a level of more than 100 dB SPL must be used for test subjects who are profoundly hard of hearing; however, test subjects with profound hearing loss are not part of the inclusion criteria for this study

Post-trial care is organized in a manner that allows the test participants to contact the sponsor site and arrange an appointment for any maintenance of the devices as needed.

A device risk analysis and risk assessment have been conducted for the new device according to EN ISO 14971. This describes the anticipated adverse device effects, residual risks associated with the investigational device and the procedures involved in its use. It also explains that the anticipated clinical benefit outweighs the potential risks. Please see the Risk Assessment for details.

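### The intervention limb of the SAE definition leaves out averted permanent impairment, so an out-patient ear or hearing event without a device deficiency that is treated in time is not an SAE

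*Protocol*

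**What the plan says.** Protocol section 10.1.1 lists what makes an adverse event serious. Apart from death and the fetal or congenital limb, an event must involve a serious deterioration in health and meet one of four limbs:

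- a life-threatening illness or injury;
- an event that "results in a permanent impairment of a body structure or a body function";
- an event that "required in-patient or prolonged hospitalisation";
- an event that "results in medical or surgical intervention to prevent life threatening illness".

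The paragraph after the list extends the definition with the words "device deficiencies that might have led to a serious adverse event if a) suitable action had not been taken or b) intervention had not been", where the sentence goes on to complete the second condition and to add a third about less fortunate circumstances. On the handling of such deficiencies it says: "These are handled under the SAE reporting system". Device deficiency is defined broadly in the same section and includes malfunction, misuse, use error and inadequate labelling.

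Section 10.1.2 attaches deadlines to these classes. SAEs, health hazards that require measures, and device deficiencies go to the sponsor within 24 hours. SAEs related or possibly related to the device or to study procedures go to the ethics committee and Swissmedic within 7 days. Health hazards that require measures are reported within 2 days.

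The protocol names several ear and hearing risks. Section 3.4 states: "The primary risk identified is the possibility of over amplification from excessive sound pressure levels". Section 3.7 addresses: "Risk of hearing loss to residual hearing at too high a level in audiological and psychoacoustic experiments". Section 10.1 includes "domes or filters falling off in the ear" among the foreseeable events.

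**The concern.** The four limbs do not fit together. Two of the outcomes that they call serious are a life-threatening injury and permanent impairment, yet treatment that prevents either one is not listed as serious. Only treatment that prevents a life-threatening illness is. The protocol gives no reason for treating one averted outcome differently from the others.

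The omission matters in this trial because the ear and hearing risks that it names threaten function more than life. For such harms the intervention limb as written will seldom apply, and the missing part is the one that would.

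Reporting time is at stake. An event that is not an SAE, a device deficiency or a health hazard is recorded as an ordinary AE with no deadline in section 10.1.2. The periodic safety report there is yearly, while the synopsis gives a study duration of about 1 to 2 months. There is no data safety monitoring committee (section 1.6) and the monitor is an employee of the sponsor (section 12.3), so expedited reports are an important outside check while participants are still in the study.

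**Working it through.** No arithmetic applies. The check takes an ear or hearing event that could have become permanent but was treated in time, and runs it through each route in sections 10.1.1 and 10.1.2.

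1. **Permanent impairment limb.** It needs the impairment to have resulted. By assumption it did not, so the limb is not met.
2. **Life-threatening limb.** Damage to hearing or the ear canal does not ordinarily threaten life, so it is not met.
3. **Hospitalisation limb.** It is met if the participant is admitted, and the event is then an SAE. Out-patient treatment does not meet it.
4. **Intervention limb.** The treatment prevented permanent impairment, not a life-threatening illness, so it is not met.
5. **Device-deficiency sentence.** If the event arose from a malfunction, misuse, use error or other inadequacy of the device, and could have led to permanent impairment without treatment, it is handled as an SAE. If there was no deficiency, the sentence does not reach it.
6. **Health hazard that requires measures.** If the finding calls for preventive or corrective measures to protect participants, it goes to the sponsor within 24 hours and is reported within 2 days. A single treated case need not meet that test.

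The three kinds of event sort as follows:

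| Averted ear or hearing event | SAE route? |
|---|---|
| Caused by a device deficiency | Yes, through the sentence after the list |
| Needs hospitalisation | Yes, through that limb |
| No deficiency, out-patient, no lasting loss | No limb is met |

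The third row is not empty by the protocol's own account. The residual-hearing risk in section 3.7 is attributed to sound levels in the tests, not to a defect of the hearing aid. Section 10.1.1 counts events related to study procedures as adverse events, and the 7-day rule in section 10.1.2 expressly covers SAEs related to study procedures. The protocol thus intends to capture procedure-related harm, but the intervention limb lets out the averted cases.

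**The case against.** The strongest reply is that most averted harms are already caught. Over-amplification through malfunction, and a dome or filter left in the ear, would plausibly count as device deficiencies. These reach the sponsor within 24 hours in any case, and they fall under SAE reporting if they might have led to an SAE. Health hazards that require measures have a shorter deadline to the authorities than SAEs. Sections 2.3 and 2.4 also call for reports of unanticipated problems that involve risks to humans. Under section 10.1 all adverse events are investigated and documented with an assessment of seriousness, so the event is not lost. Section 3.7 caps test noise at 100 dB SPL, excludes profound loss and judges the risk to be very small.

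This stands as a limit on scope and size. It does not close the third row of the table. The deficiency sentence needs a deficiency, the health-hazard route needs a finding that calls for protective measures, and sections 2.3 and 2.4 set no number of days for a single event. A risk that the protocol itself names is also hard to call unanticipated.

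A reader might go further than the text allows in four ways:

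- *Averted harms in general escape expedited review.* They do not, for the reasons just given.
- *An SAE count drives the release decision, so the gap biases it.* The protocol sets no such rule. Safety is judged from the product questionnaire and the investigator's clinical judgement (sections 4.4 and 11.4.5).
- *None of the named hazards is life-threatening.* Section 10.1 also lists a battery exploding or catching fire and traffic not being heard, so the existing limb has a use.
- *The wording departs from the ISO standard.* The protocol cites a clause, but its text is not in the document, so nothing here rests on it. Nor does the protocol name injury from taking ear impressions as a risk. That is at most an illustration of procedure-related harm.

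**Conclusion.** The point holds in a narrow form. The intervention limb is inconsistent with its neighbours. As a result, an ear or hearing event that has no device deficiency, is not hospitalised and is treated in time to avert permanent impairment is outside the SAE definition. Unless judged a health hazard that requires measures, it misses both the 24-hour and the 7-day SAE reports.

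The effect is on the timing and route of reports for rare events. No estimate or test in the analysis is affected. The protocol gives no rate for this class. Section 10.1 calls the foreseeable events improbable, section 3.7 rates the test-level risk as very small, and the synopsis plans about 15 to 20 participants, so few such events are expected, if any.

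The conclusion assumes that the limbs are applied as written. An investigator who read the intervention limb more broadly would report the event, but the text does not direct that.

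**What to change.** Extend the intervention limb in section 10.1.1 so that it covers medical or surgical intervention to prevent a life-threatening illness or injury, or a permanent impairment of body structure or function. Keep it under the existing condition of a serious deterioration in health, so that trivial events are not swept in. Before finalising, the sponsor should check the limb against the ISO 14155 clause cited there. Make the same change in the SAE form.

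The cost is one line in the protocol and one in the form, through the usual amendment route, with no extra visit, measurement or staff. The downside is that slightly more events may become reportable.
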